4.3 Exploratory Outcomes

Exploratory outcomes will include changes in characteristics related to opioid addiction including percentage of days using opioids and abstinence rates (Timeline Followback), motivation to quit (University of Rhode Island Change Assessment), craving for opioids (Visual Analog Scale), and related areas of psychiatric functioning.

- Timeline Follow-Back (TLFB; Sobell & Sobell, 1992): The TLFB obtains retrospective self-report of substance use by using a calendar and memory prompts to stimulate recall. Quantity and frequency assessments are made using this instrument (e.g., total amount of opioids used, percent of days using) as well as abstinence (yes/no). TLFB yields consistently high test-retest correlations and correlates well with other self-reports and collateral reports. The TLFB will assess consumption of opioids for 60 days prior to study entry, during the interventional phase and the follow-up phase. Use of nicotine and other drugs of abuse, including prescription drugs, will also be assessed using the TLFB.
- Urine Drug Screen (UDS) tests: Urine samples will be tested with a Multi-Drug Panel Test, which allows for the detection of THC/Marijuana, Cocaine, Phencyclidine, Opioids, Methamphetamines, Amphetamines, Barbiturates, and Benzodiazepines.
- Saliva Drug Screen tests: For follow-up visits conducted by telehealth, a Multi-Drug Panel saliva drug screen test may be optionally used in place of urine tests to facilitate ease of testing in a home setting.
- University of Rhode Island Change Assessment Scale (URICA; DiClemente & Hughes, 1999): This 32-item, self-reported questionnaire uses a five point Likert scale to assess levels of motivation to change according to the transtheoretical model (Precontemplation, Contemplation, Action, and Maintenance). This will be measured as the level of motivation to make changes may be mechanistically related to improving in opioid use.
- Visual Analog Craving Scale (VAS; McMillan & Gilmore-Thomas, 1996). At baseline, during the interventional visits, and at each follow-up visit, patients will be asked to report on the frequency, duration, and intensity of their opioid cravings on a 10 point (100 mm) VAS. This approach has been shown to yield a reliable and valid measure of craving in previous research.

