5.2 Inclusion Criteria

A subject may be eligible for enrollment if all of the following inclusion criteria apply within the thirty days prior to randomization:

- 1. Between the ages of 18 to 65 years old.
- 2. Able to provide informed consent.
- 3. Meet DSM-5 criteria for Major Depressive Disorder, without psychotic features.
- 4. Score at least 20 on the Montgomery-Asberg Depression Rating Scale.
- 5. Fulfill a minimum of 4 of 11 current opioid use disorder criteria by DSM-5.
- 6. Have used opioids illicitly at least once in the past month.
- 7. Subjects must be on a standard of care pharmacotherapy for OUD (buprenorphine, methadone or naltrexone) for at least one month.
- 8. Subjects taking other psychotropic medications (e.g. anti-depressants or non-benzodiazepine anxiolytics) must be maintained on a stable dose for at least four weeks before study initiation.
- 9. Must consent to random assignment to ketamine or placebo control.

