5.3 Exclusion Criteria

Patients will be excluded from the study if any of the following criteria apply:

- 1. They are considered an immediate suicide risk (by Columbia Suicide Severity Rating Scale of 4 or greater, a history of a suicide attempt in the past year, or by clinician judgment) or felt to be likely to require hospitalization during the course of the study.
- 2. They have a self-reported history of illicit ketamine use, or baseline urine drug testing positive for ketamine.
- 3. They are in acute opioid withdrawal (as evidenced by a score of 5 or above on the Clinician Opioid Withdrawal Scale). These subjects will be referred for clinical detoxification and pharmacotherapy induction. Subjects may be re-assessed for study eligibility after one month of treatment with a standard of care OUD pharmacotherapy.
- 4. Subjects who meet DSM-5 criteria for current bipolar disorder.
- 5. Subjects who meet DSM-5 criteria for current or history of psychotic spectrum disorders.

- 6. Women who are pregnant or nursing, and women who do not consent to use methods of highly effective birth control during the interventional phase of the study.
- 7. Subjects with current hypertension as defined by a systolic blood pressure (SBP) >140 mmHg or a diastolic blood pressure (DBP) >90 mmHg.
- 8. Subjects with a self-reported history of delirium for any cause.
- 9. A history of allergic or other adverse reaction to ketamine.
- 10. Clinically significant abnormal laboratory values, physical exam findings or self-reported medical conditions for which a transient increase in blood pressure could be significantly detrimental (e.g. glaucoma, brain aneurysms, cardiovascular disease, or end-stage renal disease).
- 11. Electrocardiogram (ECG) findings (obtained within thirty days prior to randomization) of tachycardia, prior myocardial infarction, myocardial ischemia, or aberrant conduction).

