Columbia Suicide Severity Rating Scale	Assess for presence and severity of suicidal ideation	х											
Mini International Neuropsychiatric Interview	Assess for psychotic spectrum and bipolar disorder, presence and severity of OUD	х											
Pre-screening Questionnaire	To assess for basic eligibility criteria before completing a full baseline visit.	х											
Laboratory and Procedural Tests													
Pregnancy Test (female participants only)	Eligibility assessment		х	х	х	Х	Х	х	х	х			
Drug Screen	Eligibility assessment (benzos), secondary outcome measure		х	х	х	Х	Х	х	х	х	х	х	х
Serum blood tests (CBC, CMP)	Assessment of hemodynamic, hepatic, and renal function	X**											
Electrocardiogram (ECG)	Assessment of cardiac function	X**											

* Vital signs (blood pressure, pulse, and respiratory rate) will be obtained prior to treatment sessions, and at 45 and 90 minutes post-treatment. Pulse oximetry will be monitored immediately prior to treatment, and for 90 minutes after treatment. If there is an increase in systolic or diastolic blood pressure >30 mm Hg from baseline, or an increase in pulse rate >30 bpm from baseline, the measurements should be repeated after the patient has been in a resting position for 10 minutes. ** Will be performed for individuals with significant prior cardiac, renal or liver diseases.

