10.6 Intervention Visit Procedures

Prior to administration of the study compounds, participants will complete self-report questionnaires, urine testing, and clinical assessments. They will subsequently complete a 10-minute mindfulness-based psychological relaxation exercise and fill out a questionnaire regarding their study goals. Participant will be asked to disinfect their shoulder using an alcohol wipe, and the study physician will then administer the medication by intramuscular administration into the participant's deltoid muscle. Vital signs will be monitored prior to treatment, and at 45 and 90 minutes post-treatment, and blood oxygen levels will be continuously monitored using pulse oximetry. If during the post-administration observation period, ketamine administration causes an increase in systolic or diastolic blood pressure >30 mm Hg from baseline, or an increase in pulse rate >30 bpm from baseline, the measurements should be repeated after the patient has been in a resting position for 10 minutes. If the criterion is still met, then that patient will not receive further administration of ketamine and will be withdrawn from the study. After completion of the injection, participants will be monitored for 120 minutes, during which time they will undergo debriefing and complete assessments of their perceptual experience of the intervention. We will evaluate the effects of a twice weekly interventions for 4 weeks, and monitor outcomes over an additional 4-week follow-up period to inform pharmacotherapy frequency in future clinical trials. Follow-up visits may be conducted by telehealth.

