12.2 Hypotheses for Analyses

Feasibility Hypothesis: From the cohort of individuals completing the initial prescreening assessment, a 75% study enrollment rate will be deemed feasible. Therefore, we anticipate that 40 individuals will be needed to complete prescreening so that 30 participants will enroll in the study. Of the individuals enrolling in the study, we anticipate 60% of participants will *complete* the study protocol. *Completion* is defined for the study purposes as completing at least 75% of the study visits.

Hypothesis 1: Ketamine will result in significantly greater reduction in depression symptoms as compared to placebo at one-month. To test this hypothesis, we will employ repeated measures ANOVA using linear mixed models approach to assess reduction on the total score of the MADRS.

Hypothesis 2: Ketamine will result in significantly greater reduction in frequency of opioid use as compared to placebo at one-month. To test this hypothesis, we will treat the percent days using opioids (TLFB) as a continuous variable and analyze using linear mixed models approach. Abstinence at one-week (on UDS) will be compared by intervention groups using logistical regression analyses. An arcsine square root or logit transformation may be considered to stabilize variance of the proportions.

Hypothesis 3: Response to ketamine will be influenced by changes in motivation to quit (URICA) and qualities of psychoactive perceptual experience (HMS). To test this hypothesis, we will employ repeated measures ANOVA using linear mixed models approach.

Alternate Approaches: Diagnostics of the residuals will be performed to test the assumptions of the analysis. If the assumptions are found to be inadequate, alternative methods of analysis (e.g. ordinal logistic regression or Poisson regression) will be considered.

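### The urine-screen abstinence comparison ignores pre-dose screen status, so participants whose use has not changed can count as abstinent; this dilutes the comparison but does not bias it

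*Combined protocol and SAP*

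**What the plan says.** **Outcome.** Section 12.2, Hypothesis 2: "Abstinence at one-week (on UDS) will be compared by intervention groups using logistical regression analyses". The section gives no number of screens, no drug-free period and no anchor visit. One week could mean a week after the first dose, the 1-week follow-up visit, or seven days without use. One screen at one time point is the natural reading, but the rule is not written down.

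**Entry.** Section 5.2 requires "Have used opioids illicitly at least once in the past month" and "Fulfill a minimum of 4 of 11 current opioid use disorder criteria by DSM-5". Neither sets a frequency of use beyond one occasion. No criterion asks for an opioid-positive screen. In section 5.3 the urine test excludes for ketamine: "They have a self-reported history of illicit ketamine use, or baseline urine drug testing positive for ketamine". In Table 2 (section 10.3) the purpose of the drug screen is given as "Eligibility assessment (benzos), secondary outcome measure".

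**Pre-dose screen.** Table 2 marks a drug screen at Tx1 to Tx8 and at the three follow-ups. Section 10.6 puts it ahead of the injection: "Prior to administration of the study compounds, participants will complete self-report questionnaires, urine testing, and clinical assessments". The Tx1 result is therefore a true pre-treatment value.

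**Adjustment.** Section 12.1 selects baseline covariates by whether they prove significantly related to outcomes in the trial data. The Tx1 screen is not named there or in section 12.2.

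**Standing of the analysis.** The main Hypothesis 2 variable is self-reported use: "we will treat the percent days using opioids (TLFB) as a continuous variable and analyze using linear mixed models approach". Section 4.3 places abstinence among the exploratory outcomes, although Table 2 labels the drug screen secondary. The primary outcomes in section 4.1 are feasibility measures.

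**The concern.** Someone who uses opioids on one day a month meets the opioid-use criterion and will usually screen negative on any given day, before or after dosing. If that person changes nothing, the Hypothesis 2 comparison can still count them as abstinent. The plan collects the result that would identify them, the Tx1 screen, but does not use it.

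Three things are at stake:

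- **Dilution.** Participants who would screen negative anyway cannot show an effect on this outcome, so the difference between arms shrinks.
- **Noise.** With 15 per arm, the number already negative before dosing can differ appreciably between arms by chance.
- **Interpretation.** A single abstinence rate does not separate participants who moved from positive to negative from those who were negative throughout.

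**Working it through.** **Plan's own figure.** There is none: the documents give no expected rate, detectable difference or power for urine-screen abstinence. The nearest figure, the 22% difference in section 12.3, concerns percent of days abstinent, a different variable.

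**Inputs from the documents.** 15 per arm and alpha 0.05 (section 12.3; two-sided taken); entry minimum of one use in a month (section 5.2).

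**Assumptions, not in the documents.** Detection window w = 3 days (range 2 to 4); d use-days spread at random over 30 days.

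**Step 1: chance that unchanged use gives one negative screen.** P = C(30−w, d) / C(30, d). For d = 1 and w = 3 this is 27/30 = 90%.

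| Use-days in 30 | w = 2 | w = 3 | w = 4 |
|---|---|---|---|
| 1 | 93% | 90% | 87% |
| 4 | 75% | 64% | 55% |
| 8 | 53% | 38% | 27% |
| 15 | 24% | 11% | 5% |
| 25 | 2% | 0.2% | 0% |

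If one week means seven days without use, set w = 7: a once-a-month user still passes 23/30 = 77% of the time, and a four-day user 32%.

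**Step 2: a mixed cohort.** Take d uniform on 1 to 30 (assumption) and w = 3. The mean of P over d is 22.5% (17% at w = 4, 31% at w = 2). That is the abstinence rate with no change in anyone. Treating the Tx1 and later screens as independent given d, the share of these who were also negative at Tx1 is mean(P²)/mean(P) = 54% (52% to 58%).

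**Step 3: chance imbalance.** If a proportion q is negative at Tx1, the between-arm difference has SD = √(2q(1−q)/15). At q = 0.2 this is √(0.32/15) = 14.6 points; at q = 0.5 it is √(0.50/15) = 18.3 points.

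**Step 4: dilution.** Suppose a proportion p0 would be negative anyway and ketamine makes half of the rest negative. The difference is 0.5(1−p0). Normal-approximation power with 15 per arm:

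| Background negatives p0 | Placebo v ketamine | Difference | Power |
|---|---|---|---|
| 0% | 0% v 50% | 50 points | 0.93 |
| 30% | 30% v 65% | 35 points | 0.48 |
| 65% | 65% v 82.5% | 17.5 points | 0.19 |

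**Step 5: what stratifying by Tx1 gains.** Simulation of 20,000 trials: 15 per arm, no dropout, w = 3, each day a use-day with probability d/30, ketamine cutting use-days by 75%, Mantel-Haenszel test.

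| Cohort | Unstratified | Stratified by Tx1 | Gain |
|---|---|---|---|
| d uniform on 1 to 30 | 0.68 | 0.73 | 5 points |
| 40% at 1 to 4 use-days, rest uniform on 1 to 30 | 0.43 | 0.52 | 9 points |

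With no effect, both tests reject in 0.042 to 0.049 of trials. The size of the gain depends on the assumed mix.

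**The case against.** **This is a randomised, placebo-controlled comparison.** Participants already negative fall into both arms by chance, and the test allows for that. This stands. A reader might infer that a between-arm difference could not be attributed to ketamine. The documents do not support that: allocation is randomised (section 10.5), and the unstratified test holds its 5% level in the simulation. The loss is in precision and in what the rate describes.

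**The large percentages belong to the entry minimum.** This also stands. Section 1.3 targets people who have not stayed abstinent on treatment, and section 5.2 requires at least 4 of 11 current disorder criteria. For near-daily users the problem almost disappears. One cannot say that most abstinence in this trial will be ordinary gaps in use; only that it can be, in infrequent users.

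**Other parts of the plan cover it.** Partly. The longitudinal model of percent days using, with 60 days of pre-entry use recorded (section 4.3), captures change in frequency. Section 12.1 could admit the Tx1 screen as a covariate, but only through a data-driven choice. Specific Aim 2 still names abstinence rates and urine screens as measures of efficacy.

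**A stricter definition may look like the natural remedy.** A reader might infer that abstinence should require four consecutive negative screens, for example Tx5 to Tx8. Under the Step 5 assumptions this cuts stratified power to about 0.37 in the uniform cohort and 0.43 in the mixed one, below the 0.73 and 0.52 for a single stratified screen. It also moves the time point from one week to Study Weeks 3 and 4. It needs four attended visits in a trial that expects 60% of participants to complete (defined as at least 75% of visits) and allows for up to 20% dropout.

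**Conclusion.** The point holds as a minor one. The entry criteria admit participants who are screen-negative before dosing, and section 12.2 does not use the pre-dose screen that would identify them. A participant with unchanged use can therefore count as abstinent, with a chance of about 90% (87-93%) at 1 use-day in 30, falling to 11% (5-24%) at 15. These figures rest on an assumed 2- to 4-day window and randomly spread use; the actual mix of use frequencies is unknown.

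The comparison between arms remains valid. What is lost is power, some protection against chance imbalance (SD 15 to 18 points if 20% to 50% are negative at Tx1), and a clear meaning for the abstinence rate. The analysis is exploratory and unpowered in a 30-person feasibility study, which limits the consequences.

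**What to change.** In section 12.2, prespecify the pre-dose Tx1 opioid screen (positive or negative) as a stratum or covariate in the abstinence comparison, keeping all randomised participants in the test. Report two descriptive results by arm beside it: conversion (Tx1 positive to negative) and maintenance (Tx1 negative staying negative).

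The same sentence should say which visit one week refers to, that the outcome is a single screen if that is intended, how a missing screen is handled, and how a positive result from prescribed buprenorphine or methadone is told apart from illicit use. Without the last item, Tx1 status cannot be coded consistently.

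Do not replace the single screen with a run of consecutive negatives.

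The cost is wording only, since the Tx1 screen is already scheduled. Under the Step 5 assumptions the gain is about 5 to 9 points of power with type I error still near 5%. The conversion and maintenance groups will be small with 15 per arm, so they should be presented as description, not as separate tests.

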10.3 Schedule of Assessments

The instruments to be used are standardized, have good psychometric properties, and are widely used. The schedule of study assessments is provided in **Table 2**.

Table 2: Schedule of Assessments

Table 2. Schedule of Assessments			TIME POINT										
Instrument Name	Purpose	Wk 0			(Wk6)					Wk 5 (9)	Wk 6 (10)	Wk 8 (12)	
		BL	Tx1	Tx2	Tx3	Tx4	Tx5	Tx6	Tx7	Tx8	1W F/U	2W	4W
Self-Reports and Consent											170		
Informed Consent X													
Demographics Form	Sample characterization	Х											
Concurrent Medications Form	Monitor medications	Х	Х	Х	Х	Х	Х	Х	Х	Х	Х	Х	Х
Treatment Services Tracking Form	Assess treatment engagement	х	Х	Х	Х	Х	Х	х	х	Х	Х	х	х
*Time Line Follow-Back (TLFB)	Primary Outcome: opioid use (amt. and frequency)	х	х	х	х	Х	Х	х	х	х	х	х	х
Beck Depression Inventory-II	Self-reported assessment of depression symptom severity	х	х	х	Х	Х	Х	х	х	х	х	х	х
Visual Analog Scale (VAS)	Measure subjective levels of opioid craving	х	Х	х	х	Х	Х	х	х	х	Х	Х	Х
General Anxiety Disorder (GAD-7)	Self report of anxiety symptom severity	х	Х	х	х	Х	Х	х	х	х	Х	Х	Х
Mystical Experiences Questionnaire	Measure of perceptual experiences		Х	Х	Х	Х	Х	х	х	Х			
Brief Pain Inventory	Measure of pain and quality of life	х		х		Х		х		х			х
University of Rhode Island Change Assessment (URICA)	Measure of motivation for change	х		х		х		х		х			х
Insomnia Severity Index (ISI)	Assess insomnia and sleep quality	х		х		Х		х		х			х
Five Facets of Mindfulness (FFMQ)	Assess aspects of mindfulness related	х		х		Х		х		х			х
PTSD Checklist (PCL-5)	Measure of PTSD symptoms	х		х		Х		х		х			х
Fagerstrom Test of Nicotine Dependence (FTND)	Measure of nicotine dependence	Х		х		Х		Х		х			х
Assessment of the Blind	Participant Perception of Randomization									Х			
Study goals	To characterize goals for treatment	х	х	х	х	Х	х	х	х	х			
	CI	inician	Assess	ments	n	1	1	1		1	n	n	
History and Physical Exam	Eligibility assessment	Х											
Vital Signs Measurement	Obtain readings of blood pressure, pulse, temperature, respirations and pulse oximetry	х	X*	X*	X*	X*	X*	X*	Х*	X*	х	х	х
Modified Observer Alertness/Sedation Scale (MOASS)	Measure of sedation		х	х	х	х	х	х	x	х	х		
Clinical Opioid Withdrawal Scale (COWS)	Clinician assessment of opioid withdrawal symptoms	Х											
*Montgomery-Asberg Depression Rating Scale (MADRS)	Primary Outcome: Clinician assessed measure of depression symptom severity	х		х		х		х		х	х	х	х

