12.0 DATA MANAGEMENT

12.1 Data Analysis Plan

Baseline demographic characteristics will be collected and descriptive statistics will be used to characterize participants. Data will be collected and managed using the secure REDCap (Research Electronic Data Capture) database. Descriptive statistics for primary outcomes will include 1) the percentage of individuals completing informed consent out of the number of individuals eligible on the

initial screening and 2) the percentage of individuals that complete informed consent which complete the full protocol. Other descriptive statistics for the sample population will be analyzed, and baseline characteristics that are found to be significantly associated with other outcome measures will be included as covariates. Spaghetti plots will be produced to guide modeling outcomes as a function of time. All analyses will be conducted based on intention to treat. Subjects assigned to Group B (placebo) who complete Study Wk4 (at which time main outcomes are assessed), may choose to receive 8 ketamine treatments before completing follow-up visits. To preserve study blinding, subjects who are among the final 6 subjects being enrolled will not be unblinded until primary outcomes are assessed for all 30 subjects.

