The primary dependent variables in all three analyses will be intervention group (ketamine or placebo), time (number of days), and the interaction between the two. Main hypothesis of interest will be the interaction and the post-hoc comparison at the one month after the first intervention. We anticipate the study population to include participants that are currently on antidepressants as well as those that are not. We considered stratifying randomization by this variable, however since the proporption of participants on antidepressants at baseline is expected to be small, this will be considered as an independent variable in the statistical analysis. To account for within subject correlations, several structures, such as spatial autocorrelation (to accommodate unequal time points), and AR(1) symmetry, will be examined. Diagnostics will be considered. An arcsine square root transformation may be considered to stabilize variance of the proportions. In all of the analyses, covariates will be considered to examine mediations. In a secondary analysis based on the spaghetti plots, we will consider linear and non-linear models of outcomes as a function of time. Specifically, over the 8-week follow-up period, we will examine if there exists a threshold point in time where the effect of ketamine plateaus. To achieve this, treating the joint-point as unknown, we will fit segmented regression models using non-linear mixed models.

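### The model stated for Hypothesis 3 holds no term for motivation change or perceptual experience and names no response outcome, so followed as written it does not address the hypothesis

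*Combined protocol and SAP*

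**What the plan says.** Section 12.2 states Hypothesis 3 as "Response to ketamine will be influenced by changes in motivation to quit (URICA) and qualities of psychoactive perceptual experience (HMS". The only method given is "To test this hypothesis, we will employ repeated measures ANOVA using linear mixed models approach".

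The text that follows the three hypotheses sets the model terms: "The primary dependent variables in all three analyses will be intervention group (ketamine or placebo), time (number of days), and the interaction" between them. (These are predictors, although the plan calls them dependent variables.) It then sets the test: "Main hypothesis of interest will be the interaction and the post-hoc comparison at the one month after the first intervention".

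Two sentences concern covariates. Section 12.2 says "In all of the analyses, covariates will be considered to examine mediations". Section 12.1 says that "baseline characteristics that are found to be significantly associated with other outcome measures will be included as covariates", and that all analyses follow intention to treat.

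Table 2 (section 10.3) schedules the "Mystical Experiences Questionnaire" at Tx1 to Tx8 as the measure of perceptual experience. URICA is scheduled at baseline, Tx2, Tx4, Tx6, Tx8 and the 4-week follow-up. HMS appears in Hypothesis 3 only; it is neither defined there nor listed in section 4.3 or Table 2.

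**The concern.** Hypothesis 3 concerns a relation between variables measured after randomization: do patients whose motivation rises, or who have a stronger acute experience, improve more? A group-by-time model answers a different question, namely whether the course of an outcome differs between arms. A significant interaction on URICA would show that ketamine changes motivation. It would say nothing about whether motivation change goes with improvement.

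If the plan is followed to the letter, Hypothesis 3 is either left unaddressed or settled after the data are seen, with free choice of outcome, visit, scale and model. With about 30 patients and several visits per scale, that freedom is wide. An association found that way would be hard to interpret.

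**Working it through.** **1. Which hypothesis does each reading of the stated model answer?** The terms are group, time and group-by-time. The outcome for Hypothesis 3 is not given, so take each candidate in turn.

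| Outcome put in the model | What the interaction and one-month contrast test | Addresses Hypothesis 3? |
|---|---|---|
| URICA | Whether motivation changes differently by arm | No |
| Experience score | Whether perceptual experience differs by arm; Table 2 has no baseline value, since it starts at Tx1 | No |
| MADRS total | Hypothesis 1 again | No |
| Percent days using opioids | Hypothesis 2 again | No |

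No reading relates motivation change or experience to response. Section 12.3 does define a MADRS response (a 50% reduction), but Hypothesis 3 does not refer to it, and opioid use is an equally natural reading.

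**2. Are the data there?** Yes. From Table 2 and the visit plan in section 10.1, URICA is taken at baseline and Tx4, the experience questionnaire at Tx1, and MADRS at baseline and Tx8 (study week 4). Timeline Followback is taken at every visit. Each predictor can be fixed before the outcome visit.

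**3. What precision can be expected?** The plan gives no figure for Hypothesis 3; section 12.3 sizes feasibility and Hypotheses 1 and 2 only. Inputs from section 12.3: 15 per arm, or 12 per arm with 20% dropout. For a correlation adjusted for k covariates, the Fisher z standard error is 1/√(n − 3 − k), and the 95% limits are tanh(atanh(r) ± 1.96 × SE). The r of 0.50 is an illustrative assumption.

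- Ketamine arm, adjusted for baseline MADRS (k = 1), n = 15: SE = 1/√11 = 0.302. At r = 0.50, atanh(r) = 0.549, and 0.549 ± 0.591 gives a CI of −0.04 to 0.81. With n = 12: SE = 1/√8 = 0.354, and the CI is −0.14 to 0.85.
- Both arms, adjusted for arm and baseline (k = 2), n = 30: SE = 1/√25 = 0.200, and the CI is 0.16 to 0.74. With n = 24: SE = 1/√19 = 0.229, and the CI is 0.10 to 0.76.
- Smallest within-arm correlation detectable with 80% power (two-sided 0.05, unadjusted): tanh(2.80/√12) = 0.67 with 15 patients and tanh(2.80/√9) = 0.73 with 12.

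These analyses can estimate, but can confirm only very strong relations.

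**4. Why state the covariate rule for Hypotheses 1 and 2?** First, the plan's own figure. The variance factor for the mean of 7 measures with AR(1) correlation 0.9 is 0.798, with square root 0.893. Then (1.960 + 0.842) × 15.8 × 0.893 × √(2/15) = 14.44, against 14.4 stated.

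Suppose, as an assumption, that a mediator carrying 25%, 50% or 75% of that effect were placed in the Hypothesis 1 model. The group coefficient would be 14.4 × 0.75 = 10.8, 14.4 × 0.50 = 7.2 or 14.4 × 0.25 = 3.6. It would then estimate a direct effect and not the intention-to-treat effect. The documents give no mediated share.

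**The case against.** The strongest defence is that a linear mixed model can carry URICA change and experience scores. The plan calls group, time and interaction the primary terms, not the only ones, and it mentions mediation. On that view the analysis is thinly described but capable. This stands as far as it goes: it would be wrong to say that the method cannot test Hypothesis 3. But no added term, outcome, visit or estimand is specified, and the test declared to be of main interest is the wrong one for this hypothesis.

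It is also fair to say that Hypothesis 3 is exploratory. The primary outcomes in section 4.1 are feasibility, URICA is an exploratory outcome in section 4.3, and no power is claimed for it. This limits the consequence but does not supply the missing analysis.

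Two stronger readings are tempting and are not supported:

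- **A scale with no data behind it.** A reader might infer from HMS that the perceptual data will be missing. Table 2 collects the construct with a named questionnaire at every treatment visit, so this is a label to reconcile.
- **Mediators diluting Hypotheses 1 and 2.** A reader might infer from the mediation sentence that post-randomization variables will enter the treatment-effect models. The sentence says only that covariates will be considered, for the purpose of examining mediation. The covariates that section 12.1 commits to are baseline ones. No single power loss can be quoted either. In an ANCOVA simulation with 15 per arm, power was about 77% without the mediator. With it, at an assumed 50% mediated share, power was 35% or 20%, according to whether ketamine moved the mediator by 0.8 or 1.5 SD. At 75% it was 57% or 9%. What remains is that the plan does not rule such models out.

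**Conclusion.** The concern holds as a gap in specification. The test declared for Hypothesis 3 has neither motivation change nor perceptual experience as a predictor and names no response outcome, so followed as written it does not address the hypothesis. This conclusion rests on the text alone.

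The consequence is confined to an exploratory hypothesis. Even a well-specified analysis will be imprecise, so results should be read as estimates. The precision figures assume 12 to 15 patients per arm and the Fisher z approximation.

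For Hypotheses 1 and 2, the finding is only that the place of post-randomization covariates is left open and should be closed in one sentence. The documents do not show that the treatment effect will be diluted.

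**What to change.** - **Motivation.** As an exploratory analysis, regress week 4 (Tx8) MADRS on arm, baseline MADRS and URICA change from baseline to Tx4. Do the same, separately, for percent days using opioids with its own baseline value. Report estimates with 95% CIs, and describe the result as an arm-adjusted association. It is not a mediated effect, and without an arm-by-URICA term it is not specific to ketamine.
- **Experience.** Within the ketamine arm, relate the Tx1 Mystical Experiences Questionnaire score to week 4 MADRS, adjusted for baseline MADRS, with a 95% CI. State that it rests on about 15 patients.
- **Scale name.** Reconcile HMS in Hypothesis 3 with the questionnaire in Table 2.
- **Hypotheses 1 and 2.** State that the treatment-effect models use baseline covariates only and that any mediation analysis is separate and exploratory.

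The cost is a few sentences and two small exploratory models on data already scheduled. The downside is their low precision. Tx4 and Tx1 are proposed because they precede the outcome visit; another early visit would serve if fixed before unblinding.
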